#### **(6)Celebrex group**

Celebrex capsules (Celebrex, Capsules, Pfizer Pharmaceuticals Ltd), which will be applied 1 time daily( 1 time oral 0.2g) for 4 weeks.

### **5. Outcome measurements and observe time point**

All subjects received a clinical evaluation before treatment (baseline), in treatment (2 weeks), after treatment (4 weeks), and during follow-up (3 months, 6 months) at five time points. The primary outcome measurements includes McMaster University Osteoarthritis Index (WOMAC) function score and Visual Analogue Scale (VAS); Secondary outcomes measures including WOMAC pain score, WOMAC stiffness score, the Physical Activity Scale of the Elderly (PASE), knee joint swelling measurement and WHO-BREF quality of life scale.

#### **(1) Primary outcomes**

1)Visual Analogue Scale (VAS);

2)WOMAC function score;

The primary outcome measurements will take the average of the last three days.

#### **(2) Secondary outcomes**

---

- 1)WOMAC pain score, taking the average of the last 3 days.
- 2)WOMAC stiffness score, taking the average of the last 3 days;
- 3)The Physical Activity Scale of the Elderly (PASE);
- 4)Knee joint swelling measurement;
- 5)WHO-BREF life quality scale.

(3) Acupuncture and moxibustion related safety evaluation

Stabbing pain of needle, faint, local hematoma, infection and abscess, burns, skin allergy etc. The safety assessment of acupuncture and moxibustion must be recorded after each treatment.

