## 4. Interventions

The six groups of participants (except for western medicine group) will be treated with different kinds of acupuncture treatment. **The unified needle** is the single-use, sterile steel, size 0.30×25mm or 0.30×40mm needle(Huatuo brand disposable acupuncture needle, Suzhou Medical Co., Jiangsu, China),it will be used in Ordinary acupuncture group,

---

electro-acupuncture group and Warm-needling acupuncture group; **The unified moxa** is the 2cm Yufu brand Qing Ai(Jiangsu Kangmei Pharmaceutical Co. Ltd. Jiangsu, China,Z32020253 ),it will be used in Mild moxibustion group and Warm-needling acupuncture group; **The unified Electro-acupuncture apparatuses** is the Huatuo SDZ-IIB electro-acupuncture apparatus(Jiangsu Suzhou Medical Supplies Factory LTD. Jiangsu China ),it will be used in electro-acupuncture group; **The unified Leather measuring tape** is: Type 8214 ,Size 1.5m\*7.5mm produced by Deli Group Limited; **The unified acupuncture time and therapy course** were: Each treatment lasts for 30 minutes which will be applied 3 times a week(ideally every 1 or 2 days ) for consecutive 4 weeks, 12 sessions in total; **Operator and attention:** Acupuncture treatments will be operated by the attending doctor and should pay attention to the disinfection of operator's hands and local skin before and after treatment. The treatment of acupuncture and moxibustion will be mainly aimed at the knee joint with pain symptoms, such as single or bilateral knee pain, the treatment of single / bilateral knee joint. **The unified emergency medication and treatment:** If the participants have unbearably knee pain during the study, we will allow them to take temporary emergency medication: oral Celebrex capsules (Celebrex, Capsules, Pfizer Pharmaceuticals Ltd), which will be applied once a day (0.2g a time orally).The situation of drug use should be recorded in detail; swelling of the knee joint during the test and temporary receiving treatment, but it should be recorded in detail. swelling in the knee joint effusion shown during test, allowed to accept fluid pumping treatment, but it should also be recorded in detail.

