## **(2)Statistical analysis**

- 1) the distribution of cases of six groups: the total loss rate of six groups and the loss rate due to adverse events.
- 2) comparability analysis: comparison of demographic data and other baseline values to measure the comparability of the six groups.
- 3) Compliance analysis: compared with the six groups of patients whether they meet the appropriate treatment on time and take the drug banned in the

---

programme.

4)Effectiveness analysis: main efficacy indexes are analyzed by PP (per protocol)and ITT(Intend to treat); Since this study is a multicenter clinical trial, the effect of the central effect and baseline on the efficacy index should be considered.

5)Effect factor analysis: such as age, sex, course of disease, and combination of drugs, etc.

6) Safety analysis: first, according to the requirements of adverse reaction correlation list ,describes six groups of adverse events and adverse reactions, (including the number of cases of adverse events and laboratory test indexes before and after the test , abnormal turn cases and different rate). The adverse reactions were analyzed by chi-square test.

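### Safety recording has a defined content and schedule only for needle and moxa events at each session; none is stated for the Celebrex arm, yet adverse reactions are to be tested between groups

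*Combined protocol and SAP*

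**What the plan says.** All references are to the combined protocol and SAP.

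- **Content of safety recording.** Under section 5, item (3), which follows the secondary outcomes, is headed "Acupuncture and moxibustion related safety evaluation". It lists "Stabbing pain of needle, faint, local hematoma, infection and abscess, burns, skin allergy etc".
- **Timing.** The same item states: "The safety assessment of acupuncture and moxibustion must be recorded after each treatment". No other schedule for safety recording appears.
- **Sessions.** Section 4, Interventions, sets the acupuncture and moxibustion course as "applied 3 times a week(ideally every 1 or 2 days ) for consecutive 4 weeks, 12 sessions in total".
- **Celebrex arm.** Its description gives an oral drug "which will be applied 1 time daily( 1 time oral 0.2g) for 4 weeks". It has no sessions and no safety schedule.
- **Rescue.** For unbearable knee pain during the study, section 4 says "we will allow them to take temporary emergency medication: oral Celebrex capsules". Use of the drug must be recorded; adverse events after it are not mentioned.
- **Common visits.** Section 5 gives all patients five evaluations: baseline, 2 weeks, 4 weeks, 3 months and 6 months. Adverse events are not among the measurements listed.
- **Serious events.** Section 6, Withdrawal criteria, requires immediate reporting, without restriction to any arm.
- **Analysis.** Under (2) Statistical analysis, item 6 "describes six groups of adverse events and adverse reactions", adds laboratory indexes before and after the test, and says "The adverse reactions were analyzed by chi-square test". Under (3) Statistical analysis method, Fisher's exact test is also allowed for count data.

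**The concern.** A between-group test of adverse reactions is interpretable only if the groups had a similar chance of having a reaction recorded. Here the one written procedure is tied to treatment sessions, and one of the six arms has none. The events named are mostly those of needling or burning moxa, and none is specific to an oral drug.

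If the per-session records feed the comparison, the Celebrex arm will tend to show fewer reactions for a reason unrelated to risk. That could make the drug look safer than the needle and moxa arms when it is not, or hide a real excess of drug reactions. Non-serious reactions after rescue Celebrex in the other arms are exposed to the same gap. The efficacy conclusions are not affected. What is at stake is any statement about relative safety, and the first research objective does look for a therapy that is safe as well as effective.

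**Working it through.** The plan states no adverse-event rate and no safety power, so there is no figure to reproduce. The check has two parts.

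**1. Recording occasions that the text defines, by arm, during the 4 weeks of treatment**

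| | Five needle, moxa and sham arms | Celebrex arm |
|---|---|---|
| Per-session safety recording | 3 per week × 4 weeks = 12 | 0 |
| Common evaluations (weeks 2 and 4) | 2, adverse events not listed | 2, adverse events not listed |

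Suppose adverse events are in fact asked about at the common evaluations. The session arms then have up to 12 + 2 = 14 occasions, against 2. The imbalance therefore survives the generous reading, unless the comparison is restricted to the common visits.

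**2. Illustration of what unequal recording does to the test**

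Inputs from the documents: 60 patients per arm, six arms, two-sided 0.05. Assumptions, not in the documents: the same true reaction rate p in every arm; complete recording in the five session arms; and a fraction c of events recorded in the Celebrex arm. The recorded rates are then p in five arms and c × p in the sixth.

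The test is Pearson chi-square with 6 − 1 = 5 degrees of freedom, applied to simulated binomial counts (40,000 runs per setting). For scale, p = 10% means 60 × 0.10 = 6 expected patients with a reaction per arm. With c = 50% the Celebrex arm would record 3 of them, and with c = 30% it would record 1.8.

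Share of trials in which the six-arm test rejects although true rates are equal:

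| True rate p | c = 100% | c = 75% | c = 50% | c = 25% |
|---|---|---|---|---|
| 5% | 4.5% | 5% | 7% | 10% |
| 10% | 5% | 6% | 11% | 21% |
| 20% | 5% | 8% | 23% | 61% |

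Intermediate settings:
- c = 30%: 9–10% at p = 5%, and 19% at p = 10%.
- c = 70–80%: 6–7% at p = 10%.

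With equal recording (c = 100%) the test holds its nominal level. With mild under-recording or rare events the distortion is small. It becomes material when events are common and the drug arm loses half or more of them.

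**The case against.** The strongest reply is that the plan clearly intends adverse-event data from every arm. The safety analysis names six groups and refers to a list for judging how reactions relate to treatment. It includes laboratory indexes. The case-distribution item reports losses due to adverse events in all six groups. Serious events are reportable in any arm, and the safety set requires safety data without naming arms. The per-session item can be read as a procedure-specific addition to general reporting, and its list is open-ended. The flow chart is not shown and some pages were removed, so a visit schedule may exist there.

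Most of this stands, and it rules out several stronger readings that a reader might infer:

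- *That Celebrex events go unrecorded.* The documents do not say so. What can be said is that no collection method or timing is stated.
- *That the test would nearly always be falsely significant.* Very high figures need a comparison of the drug with the other five arms pooled, which the plan does not state, or unfavourable assumptions about rate and capture. The plan does not say outright that its chi-square is a single six-arm test either, although the six-group context suggests it.
- *That a difference in needle-only events would be a false positive.* A capsule causes no needling haematoma. That is a true difference in harm, and calls for separate reporting.
- *That the trial has a comparative safety hypothesis against the drug.* The comparison with the drug in the objectives concerns efficacy; safety appears as a general aim.

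Two things do not follow from the reply. An intention to analyse six groups does not supply a collection procedure. And allowing Fisher's exact test changes the reference distribution, but leaves unequal recording as it is.

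**Conclusion.** The concern holds in limited form. In the text available, safety recording is defined in content and timing only for acupuncture and moxibustion events at sessions. No counterpart is given for the Celebrex arm or for rescue Celebrex, although adverse reactions are to be tested between groups. Equal ascertainment is therefore not assured, and a comparison that draws on the per-session records cannot separate risk from frequency of asking.

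The size is uncertain because both the event rate and the capture fraction are assumptions. Over true rates of 5–10%, the six-arm rejection rate runs from close to the nominal 5% when most drug-arm events are captured to about 19% when 30% are. It is higher only if reactions are more common or capture is poorer. The finding rests on the per-session records entering the comparison, and on the flow chart and removed pages holding no common adverse-event schedule. It should be corrected because the remedy is cheap, but it does not threaten the primary efficacy analysis.

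**What to change.** 1. In section 5, add one adverse-event item for all six arms: the same open question, covering events of any cause since the last evaluation, at the existing 2-week, 4-week, 3-month and 6-month evaluations. This also captures events after rescue Celebrex in any arm.
2. In item 6 of the statistical analysis, state that the between-arm comparison of adverse reactions uses these common records only, and name the comparison to be tested. Fisher's exact test, already allowed, suits sparse counts.
3. Keep the per-session needle and moxa records, but tabulate them separately, in the arms where each event can occur.
4. State when the laboratory tests named in the safety analysis are done, in which arms, or remove them from the analysis.

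The cost is one case-report item at visits already planned, a few lines of text and slightly more data entry. A question at 2-week or longer intervals will miss some brief events that a per-session check would catch, which is why the session records are kept. It also cannot remove every reporting difference between patients seen 12 times and patients taking a capsule at home. It does put all six arms on the same stated schedule.

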## **6. Statistical processing**

- 1)Full Analysis Set (FAS) : a collection of cases that are randomly enrolled and at least treated once.

In the analysis of the main curative effect indexes, the missing value of FAS is processed by LOCF (Last Observation Carried Forward) method, which was observed at the latest point of time. In the Case of secondary curative effect, general situation and safety Analysis, the Available Case Analysis principle is adopted to carry out missing value processing.

- 2) Per-protocol population set(PPS) : a set of cases that meet inclusion criteria and complete treatment according to the test plan. Good compliance with the test scheme and compliance ,no drug use, and the completion of efficacy evaluation(at least the primary efficacy).

- 3) Safety set (SAS) : at least one treatment, and a safety index to record the actual data.

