### **3.Inclusion criteria**

- 1)Aged 40-75 years old;
- 2) History of knee pain for more than 3 months, and complain of knee pain on most days of the past month;
- 3) I-III level in K-L classification;
- 4)At visit an average knee pain severity of 4 point or more on an 10-point VAS;
- 5)Volunteer for this test and sign informed consent.

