### **6.Withdrawal criteria**

- 1)A diagnostic physician at each center assessed the KOA exacerbations that occurred during the study. When a patient develops knee pain that cannot be alleviated by

---

acupuncture (based on VAS score > 8 points), the physician evaluates the severity and discontinues the study;

2) Onset of serious adverse events such as severe infection, coma, shock, death, etc., the main investigator should be reported immediately and the study should be suspended immediately.

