## **Analysis methods**

### **1. Sample size estimation**

Sample size estimation was by using PASS(version 11.0) software. According to document analysis and trial test, the WOMAC joint function scores could change by  $13.0 \pm 5.6$  after treatment of positive drug control group.(Qilin Liu. Observation on clinical effect of KOA by needling with moxibustion[J]. TCM clinic Research,2016,8(09):108-109.), while needling group changed by  $8.8 \pm 3.7$ (Acupuncture for Chronic Knee Pain A Randomized Clinical Trial), EA group changed by  $8.9 \pm 4.0$ (trial test), Moxibustion group changed by  $10 \pm 4.7$ (trial test), Warm needling group changed by  $12.0 \pm 6.1$ (Jianbo Wang, Yanlin Wang, Yongqi Lu, Yaochi Wu. Effect analysis of KOA by needling with moxibustion[J]. Shanghai acupuncture magazine,2010,29(06):390-392.), Sham acupuncture group changed by  $5.8 \pm 3.0$ (Acupuncture for Chronic Knee Pain A Randomized Clinical Trial). In the condition of  $\alpha=0.05$ , the power of test was  $1-\beta=0.9$  and the six groups were distributed according to 1:1:1:1:1:1 ratio, and the sample amount is at least 42. The sample size is to be expanded by estimated 20% dropout rate, and finally, there are at least 53

---

patients in each group. In view of the equality of the distribution of all cases in six centers, there were a total of 360 cases with 60 patients in each group. The following equation was used:

$$n = \psi^2 \left[ \sum_{i=1}^k s_i^2 / k \right] / \left[ \sum_{i=1}^k (\bar{X}_i - \bar{X})^2 / (k-1) \right]$$

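### Missing VAS and WOMAC function values in the FAS are filled only by LOCF, with no visit limit, no missing-data sensitivity analysis and no primary time point

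*Combined protocol and SAP*

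**What the plan says.** All references are to the combined protocol and SAP.

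- **Missing primary values** (6. Statistical processing): "In the analysis of the main curative effect indexes, the missing value of FAS is processed by LOCF (Last Observation Carried Forward) method". The carried value is the latest one observed. Available-case analysis is reserved for secondary outcomes, general situation and safety.
- **FAS** (same section): "a collection of cases that are randomly enrolled and at least treated once". No post-baseline assessment is required.
- **Visits** (5. Outcome measurements and observe time point): baseline, 2 weeks, "after treatment (4 weeks), and during follow-up (3 months, 6 months) at five time points". None is called primary. Under (1) Primary outcomes, "The primary outcome measurements will take the average of the last three days", which is a measurement rule and does not pick a visit.
- **Sample size** (1. Sample size estimation): based on WOMAC function change "after treatment of positive drug control group" and on corresponding changes in the other arms. "The sample size is to be expanded by estimated 20% dropout rate".
- **Withdrawal** (6. Withdrawal criteria, item 1): for knee pain not relieved by "acupuncture (based on VAS score > 8 points), the physician evaluates the severity and discontinues the study".
- **Analysis sets** ((2) Statistical analysis, item 4): both per-protocol (PP) and ITT analyses are listed for the main outcomes, unranked. The per-protocol set (PPS) also requires good compliance, no use of drugs and a completed primary evaluation.

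**The concern.** LOCF assumes that a patient's score stays where it was last seen. Both the needling and the drug courses last 4 weeks, so at months 3 and 6 every patient is off study treatment. A patient lost between week 4 and month 3 contributes an end-of-treatment score to both later visits. A patient lost after month 3 contributes the month-3 score at month 6. A patient lost during treatment contributes a week-2 or baseline score at week 4 and at every later visit.

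The plan expects dropout, and its withdrawal rule lets loss depend on VAS, a primary outcome. It does not say whether the VAS reading that triggers withdrawal is the value carried, or whether that reading meets the three-day-average definition.

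At stake is bias in the primary contrasts. With no primary visit and PP and ITT unranked, there is also no rule for which result counts if visits or analysis sets disagree.

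**Working it through.** **Plan's own figure.** Dropout step: 42 / (1 − 0.20) = 52.5, so 53 per group, raised to 60. This reproduces. The 20% is used only to size the trial; its timing and its split by arm are not given.

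**Inputs from 1. Sample size estimation** (mean WOMAC function gain, SD): drug 13.0, 5.6; warm-needling 12.0, 6.1; acupuncture 8.8, 3.7; sham 5.8, 3.0; 60 per arm.

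**Assumptions not in the documents.** Loss is random. A share r of the week-4 gain is kept at month 6, with r = 0.25, 0.5, 0.75 or 1 in each arm. Month-3 retention is halfway, (1 + r)/2. Correlation between visits is 0.5, with the same SD at each visit. Coverage comes from 20,000 simulated trials per case, with t intervals on 118 df.

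**Month 6.** Let dA be the share lost between week 4 and month 3 (week-4 score carried) and dB the share lost after month 3 (month-3 score carried). LOCF raises an arm's mean gain by

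g(1 − r)(dA + dB/2),

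and the shift in a contrast is the difference between its two arms. The largest positive shift has r = 0.25 in the first arm and 1 in the second, where the second arm adds nothing.

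| Timing of the 20% loss | Drug − warm-needling | Lowest coverage | Acupuncture − sham | Lowest coverage |
|---|---|---|---|---|
| All before month 3 | 13.0 × 0.75 × 0.20 = 1.95 | about 63% | 8.8 × 0.75 × 0.20 = 1.32 | about 54% |
| 10% before, 10% after | 13.0 × 0.75 × 0.15 = 1.46 | about 75% | 8.8 × 0.75 × 0.15 = 0.99 | about 69% |
| All after month 3 | 13.0 × 0.75 × 0.10 = 0.98 | about 86% | 8.8 × 0.75 × 0.10 = 0.66 | about 82% |

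Reversing the retention reverses the sign. With all loss before month 3 the shifts are −12.0 × 0.75 × 0.20 = −1.80 and −5.8 × 0.75 × 0.20 = −0.87.

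**Equal retention, all loss before month 3.** At r = 0.5 the shifts are 0.2 × (6.5 − 6.0) = 0.10 and 0.2 × (4.4 − 2.9) = 0.30, so acupuncture minus sham reads 1.80 when the truth is 1.50. Drug/warm-needling coverage stays near 95%. Acupuncture/sham coverage is about 91%, 93%, 94.5% and 95% at r = 0.25, 0.5, 0.75 and 1.

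**Completers in the same cases.** Under random loss the completer contrast has bias of about 0 and coverage of about 95%.

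**Week 4, baseline carried.** Each arm's mean gain becomes (1 − d)g, where d is the share lost.

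- 20% lost in both arms: acupuncture minus sham = 0.8 × (8.8 − 5.8) = 2.40 against 3.00 (coverage 88% to 89%); drug minus warm-needling = 0.80 against 1.00 (coverage 95%).
- 20% lost in the first arm, 10% in the second: 0.8 × 8.8 − 0.9 × 5.8 = 1.82, and 0.8 × 13.0 − 0.9 × 12.0 = −0.40.
- 10% and 20%: 0.9 × 8.8 − 0.8 × 5.8 = 3.28, and 0.9 × 13.0 − 0.8 × 12.0 = 2.10.

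**VAS.** The plan gives no means or SDs, so contrasts cannot be computed. If baseline is carried for patients withdrawn above 8, each 5% of an arm lowers its mean VAS by 0.05 × (8 − e) to 0.05 × (10 − e), where e is the entry score. The entry criterion is "At visit an average knee pain severity of 4 point or more on an 10-point VAS". At e = 4 this is 0.20 to 0.30; at e = 7 it is 0.05 to 0.15.

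**The case against.** **The PP analysis would reveal the problem.** This stands in part. A reader might infer that nothing in the plan could expose LOCF bias. The documents do not support that: PP is planned beside ITT, loss rates are to be reported for the six groups, and in the random-loss cases above completers are unbiased. A divergence could therefore be seen. But the PPS also selects on compliance and drug use, so a divergence would have several possible causes. When loss depends on pain, completers are not a safe reference either.

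**The month-3 visit limits the damage.** This stands. A reader might infer that everyone lost after week 4 carries an end-of-treatment score to month 6. The visit schedule contradicts this for patients lost after month 3, and the worst shifts then halve.

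**A mixed model is not right in every case.** This also stands. It is valid when loss depends on observed data. In a check with about 20% loss in one arm depending on the unseen month-6 gain, and random 20% loss in the other, a likelihood estimate covered about 91% to 93%. With gains fully kept, its bias for drug/warm-needling was 0.58 against 0.32 for LOCF. This supports adding a sensitivity analysis; it does not support LOCF as the only method.

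**Week 4 is implied as primary.** The sample-size wording and the visit label both point to week 4, but neither designates it.

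**Conclusion.** The point holds as a fault of specification with a plausible but unknown effect. LOCF is the sole rule for missing primary values in the FAS, it is unlimited, baseline can be carried, and no missing-data sensitivity analysis or primary visit is named.

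Under random loss after week 4, LOCF is unbiased if gains are fully kept. Otherwise it is generally biased. The month-6 figures are illustrations that rest on the plan's assumed gains, random 20% loss and assumed retention. Their low coverage values need strongly unequal retention, and 63% and 54% also need all loss to fall before month 3. With equal retention the effect is small to modest.

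A reader might infer that LOCF favours a particular arm. The documents give no loss or retention by arm, so no direction can be claimed.

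The change is worth making: it is mostly analysis-plan text, and the present rule has no planned check designed for it.

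**What to change.** 1. Replace LOCF for VAS and WOMAC function with a mixed model for repeated measures on all observed scheduled visits, with group-by-visit, baseline-by-visit and centre terms. Centre and baseline adjustment is already intended. Name the primary time point; week 4 would match the sample-size wording and the visit label.
2. Because that model is valid only if loss depends on observed data, add one multiple-imputation sensitivity analysis. It should include FAS patients with no post-baseline visit and assume worse outcomes for patients withdrawn for pain.
3. Name the FAS analysis as primary and PP as supportive.
4. Reconcile two wordings without changing any clinical rule. The PPS bar on drug use, read literally, conflicts with the permitted rescue drug and with the assigned drug of the Celebrex group. Item 3 of (2) Statistical analysis suggests that only prohibited drugs are meant, but this should be said. Also reconcile the withdrawal criterion, under which the patient leaves the study, with collecting outcomes at the scheduled visits.

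Cost: items 1 to 3 are analysis-plan changes. Item 4 needs a protocol clarification, and collecting outcomes after withdrawal would mean extra contacts at six hospitals, at a cost that the documents do not allow to be estimated. The analysis becomes slightly more complex, and confidence intervals may be somewhat wider than under LOCF.

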### (3)Statistical analysis method

1) Measurement data: first, the normal test is carried out, and t-test, paired t test, variance analysis, covariance analysis and other methods are adopted if it's in a normal distribution. Rank and inspection, matching rank and check are used for data that does not conform to normal distribution.

2) Counting data: using the chi-square test, Fisher exact test, etc.; The hierarchical data were analyzed by Ridit analysis, CMH(Cochran-mantel-Haensel statistics) or other non-parametric tests.

3) Multicenter analysis of comprehensive curative effect: using CMH method for counting data while analysis of covariance for measurement data.

4) All statistical tests were by bilateral inspection, and the P value was less than or equal to 0.05, which is statistically significant.

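### Secondary outcomes are compared on available cases and no stated method uses earlier post-baseline scores, which can leave a modest bias if response-related loss differs between arms and can put the WOMAC subscales on different patients

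*Combined protocol and SAP*

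**What the plan says.** Section 6 (Statistical processing), item 1, defines the full analysis set (FAS) as "a collection of cases that are randomly enrolled and at least treated once" and gives two missing-data rules under it. For the main efficacy indexes, "the missing value of FAS is processed by LOCF (Last Observation Carried Forward) method". For secondary efficacy, general data and safety, "the Available Case Analysis principle is adopted to carry out missing value processing".

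Section 5 decides which rule applies to which outcome. "WOMAC function score" and VAS are primary. "WOMAC pain score, taking the average of the last 3 days" is secondary, as are WOMAC stiffness, PASE, knee swelling and WHO-BREF. All are measured at baseline, weeks 2 and 4, and months 3 and 6.

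Under (3) Statistical analysis method, item 1 says that for normally distributed data "t-test, paired t test, variance analysis, covariance analysis and other methods are adopted"; item 3 assigns analysis of covariance to measurement data in the multicentre analysis. Under (2) Statistical analysis, item 4 asks that centre and baseline be considered, and names PP and ITT analyses for the main efficacy indexes only. No section gives an imputation, a longitudinal model or a sensitivity analysis for the secondary outcomes.

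The withdrawal criteria let a physician discontinue a patient whose knee pain is not relieved by "acupuncture (based on VAS score > 8 points").

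**The concern.** An available-case comparison at, say, week 4 uses only patients measured at week 4. If those missing had been doing badly, the mean of the remaining patients is too favourable. When this happens to a similar extent in both arms it largely cancels; when one arm loses more poor responders, that arm looks better than it is. The withdrawal criteria make response-related loss plausible. Unequal loss is plausible too: the sample size section assumes mean improvements from 5.8 (sham) to 13.0 (drug).

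The information that would reduce this bias is already scheduled. A patient missing at week 4 often has a week-2 score, but no stated method uses it.

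The two rules also split one questionnaire. At a missed visit WOMAC function is filled in, while WOMAC pain and stiffness are left out. If function and pain then disagree, a reader cannot tell whether the treatment or the missing-data rules caused it.

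**Working it through.** **1. The plan's own figure.** The only stated figure that bears on loss is the inflation for 20% dropout (section 1, Sample size estimation): 42 / (1 − 0.20) = 52.5, rounded up to 53 per group. This reproduces. The plan then takes 60 per group.

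**2. Patients counted at a visit.** If the full 20% is missing at one visit, 60 × 0.20 = 12 per arm are missing and 48 remain. Over six arms, 360 × 0.80 = 288 are counted for WOMAC pain and stiffness, against up to 360 for WOMAC function with LOCF. The 12 is an upper figure at that loss rate, since patients never treated leave the FAS for every outcome.

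**3. Bias without adjustment.** Assumptions, none from the documents: normal scores with SD 1, no true difference, the worst fraction q at week 2 missing at week 4, correlation ρ = 0.5 to 0.7 between the two visits. With a = z_q, the week-2 mean of those remaining shifts by λ = φ(a)/(1 − q):

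| q | 10% | 15% | 20% | 25% | 30% |
|---|---|---|---|---|---|
| λ | 0.195 | 0.274 | 0.350 | 0.424 | 0.497 |

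The false difference at week 4 is ρ × D, where D is the difference in λ between arms.
- 15% v 25%: D = 0.149; bias 0.07 to 0.10 SD.
- 10% v 30%: D = 0.302; bias 0.15 to 0.21 SD. Simulation with 60 per arm gives about 12 to 22% false positives at nominal 5%.
- 20% v 20%: D = 0; bias zero.

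**4. Bias with baseline adjustment, which the plan allows.** Assume baseline correlates 0.5 with each visit. The bias becomes (ρ − 0.5b) × D, where b is the within-arm slope of week 4 on baseline among those remaining: b = (0.5 − 0.5ρd)/(1 − 0.25d). Here d is the average over the two arms, weighted by patients remaining, of λ(λ − a). It is 0.409 for 15% v 25% and 0.384 for 10% v 30%.

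| Loss | ρ | b | Bias (SD) |
|---|---|---|---|
| 15% v 25% | 0.5 | 0.443 | (0.5 − 0.221) × 0.149 = 0.04 |
| 15% v 25% | 0.7 | 0.397 | (0.7 − 0.199) × 0.149 = 0.07 |
| 10% v 30% | 0.5 | 0.447 | (0.5 − 0.224) × 0.302 = 0.08 |
| 10% v 30% | 0.7 | 0.404 | (0.7 − 0.202) × 0.302 = 0.15 |

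Simulated false-positive rates are 5 to 7% for 15% v 25% and 7 to 14% for 10% v 30%. Repeat runs moved the upper ends by one or two percentage points.

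**5. Softer loss.** If poor week-2 scores only raise the chance of loss (logit slope 0.5 to 1 per SD), the adjusted bias is about 0.02 to 0.04 SD at 15% v 25% and 0.02 to 0.08 SD at 10% v 30%, with 5 to 7% false positives.

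**6. Using the week-2 score.** In the same simulations an estimate that uses the week-2 score has bias of 0.01 SD or less. This follows from letting loss depend on week 2 alone.

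**7. Direction.** The documents give no change scores for pain or stiffness, so take the sample-size figures for function as a stand-in: needling 8.8 (SD 3.7), sham 5.8 (SD 3.0), difference 3.0. If loss removes the worst responders on the outcome itself:
- 10% (needling) v 30% (sham): (8.8 + 3.7 × 0.195) − (5.8 + 3.0 × 0.497) = 9.52 − 7.29 = 2.23.
- 30% v 10%: 10.64 − 6.38, a difference of 4.25 before rounding.
- 20% v 20%: 10.09 − 6.85 = 3.24. The small residue comes from the unequal SDs.

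The bias can go either way.

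**The case against.** The strongest case on the other side has five parts.

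- **The plan does use earlier scores.** A reader might infer that the named tests ignore everything before the visit. They do not: covariance analysis is listed and baseline is to be considered. This stands, and it cuts the bias by about 30 to 45% (steps 3 and 4). What remains is that no stated method uses intermediate visits.
- **Patients do not disappear.** A reader might infer that a lost patient leaves the secondary analyses altogether. Available-case analysis keeps every attended visit. Both rules also sit under one FAS definition, so the nominal population is the same; only the patients counted at a missed visit differ.
- **Outcome-related loss need not bias the comparison.** Equal loss gives almost none. The plan has a single 20% allowance with no split by arm, so unequal loss is an assumption. Losing only the worst scorers is an extreme one.
- **The withdrawal rule does not show that loss follows recorded scores.** It concerns an exacerbation judged by a physician, is not tied to a scheduled visit, and does not say whether measurement stops. A flare between visits may never enter the data, and a repeated-measures model would then be biased too. The near-zero result in step 6 is therefore a best case.
- **These are secondary outcomes.** The primaries have both PP and ITT analyses, and loss rates are to be reported for the six groups, so unequal loss would be visible.

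All five limit the size of the point. None supplies a missing-data method for the secondary outcomes that uses intermediate visits, or removes the split between WOMAC subscales.

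**Conclusion.** The point holds in a limited form. The available-case rule discards usable week-2 and later scores, and baseline adjustment recovers only part of what is lost. With 60 per arm, no true difference and the assumed correlations, the remaining bias is 0.04 to 0.15 SD under worst-scorer loss at the two unequal splits tried. Neither those splits nor the correlations come from the documents. The larger unadjusted figures in step 3 should not be read as the plan's expected error, because the plan provides for baseline adjustment.

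The split within the WOMAC follows directly from the stated rules and needs no assumption; only its extent, up to about 12 of 60 per arm, depends on the loss at that visit.

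The change is worth making because it is cheap and WOMAC pain is an important supporting outcome in this trial. The documents do not support a claim that the secondary results will be biased, or in which direction.

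**What to change.** For the continuous secondary outcomes, replace the available-case rule with one likelihood-based repeated-measures model per outcome:
- visits: weeks 2 and 4, months 3 and 6;
- terms: arm, visit, arm-by-visit, centre, baseline, baseline-by-visit;
- unstructured covariance;
- all FAS patients with any post-baseline value.

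Keep the available-case result as a sensitivity analysis. Run the same model for WOMAC function as a supporting analysis, so that the three subscales can be compared on the same patients. The primary LOCF rule is outside this point. Extending LOCF to the secondary outcomes would align the sets but would not solve response-related loss.

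Cost: a few lines of SAP text and modest programming, with no new data. The model is unbiased only if loss is explained by recorded scores; an unrecorded flare between visits would still bias it.
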